#### **4.6.3 Study and Site Discontinuation**

The Sponsor has the right to terminate this study at any time. Reasons for terminating the study may include, but are not limited to, the following:

- The incidence or severity of adverse events in this or other studies indicates a potential health hazard to patients.
- Patient enrollment is unsatisfactory.

The Sponsor will notify the investigators if the Sponsor decides to discontinue the study.

The Sponsor has the right to close a site at any time. Reasons for closing a site may include, but are not limited to, the following:

- Excessively slow recruitment
- Poor protocol adherence
- Inaccurate or incomplete data recording
- Non-compliance with the International Council for Harmonisation (ICH) guideline for GCP
- No study activity (i.e., all patients have completed the study and all obligations have been fulfilled)

### **5. ASSESSMENT OF SAFETY**

#### **5.1 SAFETY PLAN**

Polatuzumab vedotin is not a marketed product, and *lenalidomide* is not approved for the treatment of patients with R/R FL. *Obinutuzumab* is only approved in combination with bendamustine for the treatment of R/R FL. *Rituximab* and *lenalidomide* are not approved for the treatment of patients with R/R DLBCL. Clinical development is ongoing. The safety plan for patients in this study is based on clinical experience with *obinutuzumab*, *rituximab*, *polatuzumab vedotin*, and *lenalidomide* in completed and ongoing studies. The anticipated important safety risks of *obinutuzumab*, *rituximab*, *polatuzumab vedotin*, and *lenalidomide* are outlined below. Please refer to the *Obinutuzumab*, *Rituximab*, and *Polatuzumab Vedotin Investigator's Brochures* and the

lenalidomide Summary of Product Characteristics (SmPC) for a complete summary of safety information.

Several measures will be taken to ensure the safety of patients participating in this trial. Eligibility criteria have been designed to exclude patients at higher risk for toxicities (see Section 4.1). Patients will undergo adequate safety monitoring during the study, including assessment of the nature, frequency, and severity of adverse events, as described in this section and in Section 4.5. In addition, guidelines for managing adverse events, including criteria for dosage modification and treatment delays or discontinuation, have been provided (see Section 5.1.7).

### **5.1.1 Risks Associated with Obinutuzumab**

To date, the following adverse events are considered to be important *identified* risks associated with obinutuzumab: IRRs, TLS, thrombocytopenia (including acute thrombocytopenia), neutropenia (including prolonged and late onset neutropenia), infections (including PML and HBV reactivation), prolonged B-cell depletion, impaired immunization response, worsening of preexisting cardiac conditions, and gastrointestinal perforation.

#### **5.1.1.1 Infusion-Related Reactions**

IRRs have been reported predominantly during the first infusion of obinutuzumab. The incidence and severity of IRRs decreased substantially with the second and subsequent infusions. In the majority of patients, IRRs were mild or moderate and resolved with the slowing or interruption of the infusion and supportive care. The commonly experienced IRRs have been characterized by hypotension, fever, chills, flushing, nausea, vomiting, hypertension, fatigue, and other symptoms.

IRRs may be clinically indistinguishable from IgE-mediated allergic or anaphylactic reactions; anaphylaxis has been reported in patients treated with obinutuzumab.

Hypotension may occur during obinutuzumab IV infusions. Therefore, withholding of antihypertensive treatments should be considered for 12 hours prior to and throughout each obinutuzumab infusion and for the first hour after administration. Patients at acute risk of hypertensive crisis should be evaluated for the benefits and risks of withholding their antihypertensive medication.

Patients who have preexisting cardiac or pulmonary conditions should be monitored carefully throughout the infusion and the post-infusion period.

Guidelines for medical management of IRRs and anaphylaxis are provided in Section 4.3.2.1 and Appendix 8.

### **5.1.1.2 Tumor Lysis Syndrome**

TLS, including fatal events, has been reported with obinutuzumab administration. Patients at risk for TLS (e.g., because of bulky disease or renal insufficiency) should receive adequate hydration and premedication with allopurinol or an alternative uricostatic agent as indicated in Section 4.3.2.5 (see Table 13). Additional guidelines for management of TLS in this study are provided in Section 5.1.7.3 (see Table 19).

### **5.1.1.3 Neutropenia**

Grade 3 or 4 neutropenia, including febrile neutropenia, has been reported with obinutuzumab administration. Neutropenia resolved spontaneously or with use of hematopoietic growth factors. Patients who experience Grade 3 or 4 neutropenia should be closely monitored until neutrophil values return to at least Grade 2. Cases of late-onset neutropenia (ANC < 1000 cells/ $\mu$ L occurring  $\geq$  28 days after obinutuzumab treatment has been completed or stopped) or prolonged neutropenia (ANC < 1000 cells/ $\mu$ L that does not resolve after 28 days without obinutuzumab treatment) have also been reported. The use of G-CSF is allowed for treatment of neutropenia in this study. Prophylactic treatment with antibiotics should be administered as per standard practice. Guidelines for primary prophylaxis with G-CSF are provided in Section 4.4.1.

### **5.1.1.4 Thrombocytopenia**

Severe and life-threatening thrombocytopenia, including acute thrombocytopenia (occurring within 24 hours after the infusion), has been observed during treatment with obinutuzumab. In patients with CLL exposed to obinutuzumab, fatal hemorrhagic events have also been reported in Cycle 1. A clear relationship between thrombocytopenia and hemorrhagic events has not been established. Patients receiving concomitant medication that could possibly worsen thrombocytopenia-related events (e.g., platelet inhibitors and anticoagulants) may be at greater risk of bleeding. When possible, replace prior vitamin K antagonist therapy with LMWH prior to Day 1 of Cycle 1. Patients should be closely monitored for thrombocytopenia, especially during the first cycle. For patients who experience thrombocytopenia, regular laboratory tests should be performed until the event resolves, and dose delays should be considered in case of severe or life-threatening thrombocytopenia. Transfusion of blood products (i.e., platelet transfusion) may be performed at the discretion of the treating physician, according to institutional practice.

### **5.1.1.5 Infections**

On the basis of its mechanism of action, resulting in profound B-cell depletion, obinutuzumab may be associated with an increased risk of infections. Obinutuzumab should not be administered to patients with active infection, and caution should be exercised when including patients with a history of recurrent or chronic infections.

Serious bacterial, fungal, and new or reactivated viral infections can occur during and following the completion of obinutuzumab therapy. Fatal infections have been reported.

Reactivation of hepatitis B in patients with chronic hepatitis (HbsAg positive) with evidence of prior hepatitis B exposure, or in patients who are carriers (HbsAg negative and anti-HBc positive) has been reported with other anti-CD20 antibodies. The risk is increased particularly when anti-CD20 antibodies are administered with immunosuppressive therapies, such as steroids or chemotherapy. Patients positive for HbsAg or HbcAb are not eligible for this study.

JC viral infection resulting in PML has been reported in patients treated with obinutuzumab. The diagnosis of PML should be considered in any patient presenting with new-onset neurologic manifestations. The symptoms of PML are unspecific and can vary depending on the affected region of the brain. Motor symptoms with corticospinal tract findings (e.g., muscular weakness, paralysis, and sensory disturbances), sensory abnormalities, cerebellar symptoms, and visual field defects are common. Some signs or symptoms regarded as “cortical” (e.g., aphasia or visual-spatial disorientation) may occur. Evaluation of PML includes, but is not limited to, consultation with a neurologist, brain MRI, and lumbar puncture (cerebrospinal fluid testing for JC viral DNA). Additional guidelines for medical management of PML in this study are provided in Section 5.1.7.

#### **5.1.1.6 Immunizations**

The safety of immunization with live *or attenuated viral* vaccines following obinutuzumab therapy has not been studied *and* vaccination with live virus vaccines is not recommended during treatment and until B-cell recovery.

#### **5.1.1.7 Worsening of Preexisting Cardiac Condition**

In patients with underlying cardiac disease and treated with obinutuzumab, adverse events such as angina pectoris, acute coronary syndrome, myocardial infarction, heart failure, and arrhythmias, including atrial fibrillation and tachyarrhythmia, have been observed. These events may occur as part of an IRR and can be fatal. Therefore, patients with a history of cardiac disease should be monitored closely. In addition, these patients should be hydrated with caution to prevent a potential fluid overload.

#### **5.1.1.8 Gastrointestinal Perforation**

GI perforation has been reported in patients with B-cell lymphoma treated with obinutuzumab, including fatal events. Patients with GI involvement should be monitored for signs of GI perforation.

### **5.1.2 Risks Associated with Rituximab**

*The following adverse events are considered to be important risks associated or potentially associated with rituximab: IRRs, infections (including severe infections), PML, hepatitis B reactivation, neutropenia (including prolonged neutropenia), TLS, impaired immunization response, severe skin reactions (Stevens-Johnson syndrome [SJS]/toxic epidermal necrolysis [TEN]), and GI perforation. Details for these risks are provided below; refer to the Rituximab Investigator’s Brochure for full information.*

### **5.1.2.1 Infusion-Related Reactions**

Acute IRRs are very common in patients receiving rituximab (occurring in  $\geq 10\%$  of patients) based on clinical trial experience. However, serious IRRs are uncommonly reported (occurring in  $\geq 1$  of 1,000 and  $< 1$  of 100 patients) and are rarely fatal (occurring in  $\geq 1$  of 10,000 and  $< 1$  of 1,000 patients). Most IRRs occur with the first administration of rituximab. Most IRRs are mild to moderate in severity (Grades 1 or 2) and can be managed by slowing or stopping the rituximab infusion. IRRs can be severe and, in rare cases, can result in death. Rituximab-induced IRRs consist of a cluster of symptoms and signs occurring during or within 24 hours of a rituximab infusion that may be related to cytokine release and/or other chemical mediators, and these acute IRRs overlap with “cytokine release syndrome.” Anaphylactic and other hypersensitivity reactions have been reported following rituximab administration, and clinical manifestations of these reactions are similar to cytokine release syndrome. In contrast to cytokine release syndrome, true hypersensitivity reactions typically occur within minutes of starting the rituximab infusion.

### **5.1.2.2 Infections (Including Serious Infections)**

Serious infections, including fatal bacterial, fungal, and new or reactivated viral infections, can occur during and up to 1 year following completion of rituximab-based therapy.

### **5.1.2.3 Hepatitis B Reactivation**

Reactivation of hepatitis B ranges from asymptomatic reactivations (detected by changes in laboratory parameters only) to fulminant liver failure and death. Patients with chronic hepatitis B (HBsAg positive) viral infection are at risk for reactivation and will be excluded from the study. Patients with evidence of prior hepatitis B exposure or who are carriers (defined as HBsAg negative and anti-HBcAb positive) are at a lower risk for reactivation. Patients who demonstrate evidence of reactivation while receiving an appropriate anti-viral therapy will be discontinued from study treatment.

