## 2. **OBJECTIVES AND ENDPOINTS**

This study will evaluate the safety, efficacy, and pharmacokinetics of induction treatment consisting of obinutuzumab in combination with polatuzumab vedotin and lenalidomide (G+Pola+Len) in patients with R/R FL *and rituximab in combination with polatuzumab vedotin and lenalidomide (R+Pola+Len) in patients with R/R DLBCL*, followed by post-induction treatment with G+Len (*referred to as maintenance*) in patients with FL who achieve a CR, PR, or stable disease at EOI and *post-induction treatment with rituximab plus lenalidomide (R+Len; referred to as consolidation)* in patients with DLBCL who achieve a CR or PR at EOI. Specific objectives and corresponding endpoints for the study are outlined below.

In this study, "study treatment" refers to the protocol-mandated treatments under study (i.e., obinutuzumab, *rituximab*, polatuzumab vedotin, and lenalidomide).

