- Positive for hepatitis B surface antigen (HBsAg), total hepatitis B core antibody (HBcAb), or hepatitis C virus (HCV) antibody at screening
- Known history of HIV positive status
  - For patients with unknown HIV status, HIV testing will be performed at screening if required by local regulations.
- History of progressive multifocal leukoencephalopathy
- Vaccination with a live virus vaccine within 28 days prior to Day 1 of Cycle 1
- History of other malignancy that could affect compliance with the protocol or interpretation of results, with the exception of the following:

Curatively treated carcinoma in situ of the cervix; good-prognosis ductal carcinoma in situ of the breast; basal- or squamous-cell skin cancer; Stage I melanoma; or low-grade, early-stage localized prostate cancer

Any previously treated malignancy that has been in remission without treatment for  $\geq 2$  years prior to enrollment

- Contraindication to treatment for TE prophylaxis (see Section 4.3.2.5)
- Grade  $\geq 2$  neuropathy
- Evidence of any significant, uncontrolled concomitant disease that could affect compliance with the protocol or interpretation of results, including significant cardiovascular disease (such as New York Heart Association Class III or IV cardiac disease, myocardial infarction within the previous 6 months, unstable arrhythmia, or unstable angina) or significant pulmonary disease (such as obstructive pulmonary disease or history of bronchospasm)
- Major surgical procedure other than for diagnosis within 28 days prior to Day 1 of Cycle 1 or anticipation of a major surgical procedure during the course of the study
- Inadequate hematologic function (unless due to underlying lymphoma), defined as follows:
  - Hemoglobin  $< 9$  g/dL
  - ANC  $< 1.5 \times 10^9/L$
  - Platelet count  $< 75 \times 10^9/L$
- Any of the following abnormal laboratory values (unless due to underlying lymphoma):
  - Calculated creatinine clearance  $< 50$  mL/min (using the Cockcroft-Gault formula; see Appendix 7)
  - AST or ALT  $> 2.5 \times ULN$
  - Serum total bilirubin  $> 1.5 \times ULN$  (or  $> 3 \times ULN$  for patients with Gilbert syndrome)
  - INR or PT  $> 1.5 \times ULN$  in the absence of therapeutic anticoagulation
  - PTT or aPTT  $> 1.5 \times ULN$  in the absence of a lupus anticoagulant
- Pregnant or lactating, or intending to become pregnant during the study

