### **4.6.2 Study Treatment Discontinuation**

Study treatment should be permanently discontinued in patients who experience any of the following:

- Anaphylaxis, acute respiratory distress, or Grade 4 IRR  
If a Grade 3 IRR is recurrent during the second or subsequent cycles, study treatment may be discontinued at the discretion of the investigator, following an individual benefit-risk assessment.
- Any adverse event that meets criteria for permanent discontinuation per guidelines provided in Section 5.1
- Pregnancy
- Disease progression

The primary reason for study treatment discontinuation should be documented on the appropriate eCRF.

Patients who discontinue study treatment will not be replaced, except as outlined below:

- During the dose-escalation phase, patients who discontinue study treatment prior to completing the DLT assessment window for reasons other than a DLT will be replaced by an additional patient at that same dose level.
- Patients who discontinue prior to receiving at least one dose of each component of the combination will be replaced.

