### Non-Hematologic Toxicities during Induction Treatment

[Table 19](#) provides guidelines for management of non-hematologic toxicities that occur during induction treatment.

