**Table 19 Guidelines for Management of Non-Hematologic Toxicities During Induction**

Event		Action to Be Taken
General guidance for treatment delays and discontinuation		
 
– If study treatment is withheld for >21 days because of a toxicity that is attributable to study treatment, permanently discontinue study treatment.
 
– When a treatment cycle is delayed because of toxicity resulting from any component of the regimen, all study treatment should be held and resumed together to remain synchronized.
 
– If one drug is discontinued, treatment with the other two drugs may be continued for patients experiencing clinical benefit as determined by the investigator after discussion with the Medical Monitor.
 

IRRs and anaphylaxis		
 
– Guidelines for the management of IRRs are provided in Section 4.3.2.1 for obinutuzumab, Section 4.3.2.2 for rituximab, and Section 4.3.2.3 for polatuzumab vedotin.
 
– In case of anaphylaxis, study treatment should be permanently discontinued.
 

Renal toxicity		
 
– Adjust the dose of lenalidomidea as outlined below: 
 
• If creatinine clearance is <math>\geq 30</math> but <math>< 50</math> mL/min, lenalidomide should be given at a dose of 10 mg/day.
 
• If creatinine clearance is <math>< 30</math> mL/min and dialysis is not required, lenalidomide should be given at a dose of 10 mg every other day.
 
• If creatinine clearance is <math>< 30</math> mL/min and dialysis is required, lenalidomide should be given at a dose of 5 mg/day. On dialysis days, the dose should be administered after dialysis.
 
 
 

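### The only hepatitis B reactivation stop depends on the patient already receiving anti-viral therapy, which hardly fits the enrolled population; other reactivations fall to generic rows that return the anti-CD20 antibody on grade recovery

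*Combined protocol and SAP*

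**What the plan says.** Section 5.1.2.3, under the rituximab risks, describes reactivation as ranging from laboratory changes alone to fulminant liver failure and death. It then gives one treatment rule: "Patients who demonstrate evidence of reactivation while receiving an appropriate anti-viral therapy will be discontinued from study treatment".

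Section 4.1.2 excludes any patient "Positive for hepatitis B surface antigen (HBsAg), total hepatitis B core antibody (HBcAb), or hepatitis C virus (HCV) antibody at screening", and Section 5.1.1.5 repeats this for hepatitis B: "Patients positive for HbsAg or HbcAb are not eligible for this study". The protocol prescribes no hepatitis B prophylaxis.

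Section 4.6.2 lists reasons for permanent discontinuation. It does not name hepatitis B, but it includes "Any adverse event that meets criteria for permanent discontinuation per guidelines provided in Section 5.1", which brings in whatever Section 5.1 and its tables say. Section 2 states that the term study treatment "refers to the protocol-mandated treatments under study", meaning all four drugs.

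For obinutuzumab, Section 5.1.1 lists hepatitis B reactivation among the infections that are identified risks, and Section 5.1.1.5 adds: "Obinutuzumab should not be administered to patients with active infection".

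Table 19 "provides guidelines for management of non-hematologic toxicities that occur during induction treatment". Table 20 covers consolidation and maintenance. Neither has a hepatitis B row.

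**The concern.** The stop applies to reactivation that occurs despite anti-viral cover. That condition suits a trial that enrols HBcAb-positive carriers and gives them prophylaxis, but this trial excludes them. A reactivation here would arise from an infection that screening missed or that was occult, in someone with no reason to be taking an anti-viral. Read literally, the rule is then silent and the event is managed like any other liver or non-hematologic toxicity. The decision to give more B-cell-depleting antibody would turn on the toxicity grade, and for rituximab no written condition asks whether the virus is controlled. By the protocol's own account, the worst outcome is fatal.

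**Working it through.** No figure in the plan is at issue, so the check sets the rules side by side for a patient who reactivates while not on an anti-viral.

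**Induction (Table 19)**
- AST, ALT or bilirubin increase, Grade 3 or worse: withhold, monitor, investigate the cause. On recovery to Grade 1 or better, the antibody and polatuzumab vedotin resume at full dose and lenalidomide at a reduced dose. Life-threatening liver toxicity is a permanent stop.
- Other non-hematologic toxicity: Grade 4 is a permanent stop. For Grade 2 or 3, withhold, then resume the antibody on recovery to Grade 1 or baseline.
- Any hold longer than 21 days "because of a toxicity that is attributable to study treatment, permanently discontinue study treatment".

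**Post-induction (Table 20)**
- Non-hematologic toxicity, Grade 2 or worse: withhold, then give study treatment at full dose on recovery to Grade 1 or baseline. The only permanent stop is a hold longer than 42 days. The row contains no Grade 4 stop, no life-threatening-liver stop and no instruction to look for a cause.

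**Is viral status a condition for resuming?** In none of these rows. By contrast, suspected PML has its own row in Table 19: treatment resumes only if PML is ruled out and stops for good if it is confirmed. Section 5.2.5 names PML and hepatitis B reactivation together as the two events that need additional data collection, yet only PML has a treatment rule in the table.

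**Would reactivation be recognised?** Section 4.5.6 defines the hepatitis B tests as HBsAg and total HBcAb, and Appendices 1 and 2 place them at screening only. Table 19 asks for the cause of a liver event without naming these tests.

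**Does the answer differ by antibody?**
- Obinutuzumab: reactivation is classed as an infection (Section 5.1.1) and dosing during active infection is barred (Section 5.1.1.5). Together these add an infection-status condition to the grade rows. It is a bar on dosing, not a discontinuation rule.
- Rituximab: Section 5.1.2.2 describes serious infections but contains no such bar. The conditional sentence in Section 5.1.2.3 is the only reactivation-specific rule.

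The gap is therefore widest for rituximab patients and, within the tables, after induction.

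**The case against.** The strongest reply is that much is already in place. Severe or prolonged events stop treatment through the generic rows. Liver injury meeting Hy's law is reportable within 24 hours (Sections 5.2.3 and 5.3.5.7), the Internal Monitoring Committee reviews cumulative safety data, and the investigator may withdraw a patient for safety. Anti-virals are not prohibited. If one is started and reactivation persists, Section 5.1.2.3 can then apply. Section 5.1.7 lets one drug be stopped while the others continue, so dropping the antibody alone is open to the investigator. The Investigator's Brochures, which are not available here, may give further guidance. All of this stands and limits the size of the problem. It does not supply a rule: these provisions act on grade, duration or judgment, and no passage tells the site to start an anti-viral or to withhold rituximab because of reactivation itself.

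Some stronger readings are tempting and are not supported:
- A reader might infer that obinutuzumab patients would also be re-dosed whatever their viral status. The active-infection bar says otherwise. Section 2 and Section 4.6.2 also leave it unclear, rather than ruled out, whether the Section 5.1.2.3 stop reaches them.
- A reader might infer that the post-induction hold limit is laxer because it is 42 days and not 21. Relative to the antibody interval it is unchanged: 21/28 = 75% in induction, and 42/(2 × 28) = 42/56 = 75% afterwards, since a month is defined as 28 days.
- Resuming at full dose may look aggravating. Section 5.1.7 allows no dose reduction of either antibody, so full dose is the only dose there is.
- Section 5.1.2.3 calls only HBsAg-positive patients excluded and describes HBcAb-positive carriers as lower risk. This might suggest that carriers can enrol. Sections 4.1.2 and 5.1.1.5 exclude them, so the mismatch is editorial.

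**Conclusion.** The point holds as a minor safety-rule correction. The one reactivation-specific stop depends on a condition that the enrolled patients would seldom meet, and the rows that apply instead return the anti-CD20 antibody on grade recovery. It matters mainly for rituximab, and for the post-induction period, where Table 20 has no Grade 4 or life-threatening-liver stop for non-hematologic toxicity.

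The documents give no rate of reactivation or of anti-viral use. That most reactivations would begin off anti-virals is an inference from the two serologic exclusions and the absence of prescribed prophylaxis. The same exclusions mean that few events are expected, possibly none. Harm would also require the event to recover within the hold limit and the investigator to re-dose. Sample size, the primary endpoint and its estimate are untouched.

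**What to change.** At the next amendment:

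1. In Section 5.1.2.3, remove the anti-viral condition. State that confirmed reactivation in a patient receiving obinutuzumab or rituximab, whatever the anti-viral status, leads to withholding all study treatment, starting anti-viral therapy and permanently discontinuing the anti-CD20 antibody. Keep the present rule that all study treatment stops if reactivation occurs or persists on anti-viral therapy.
2. Put that rule in one row of Table 19 and one row of Table 20, stated to override the AST/ALT/bilirubin row and the other generic resume rows.
3. Require hepatitis B testing in the work-up of any liver event that triggers a hold, in both periods, and say which result counts as confirmed reactivation.
4. Align Section 5.1.2.3 with the HBcAb exclusion in Section 4.1.2 (editorial).

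The cost is two table rows, a few sentences, and repeat tests only in patients held for a liver event. The downside is that a rare patient whose reactivation resolves loses the remaining anti-CD20 doses. That is a real loss for FL patients, who enter because the investigator sees no more appropriate option, but it is small against the outcome the rule guards against.
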